9.2. Populations for Analyses

All data analyses will be performed using at least 1 of the following analysis sets.

Analysis Set	Description
Enrolled Analysis Set	All participants who sign an ICF and are provided with an enrollment number. The Enrolled Analysis Set will be used for all participant disposition analyses.
Safety Analysis Set	All participants who received at least 1 dose of study drug. Participants will be classified according to actual intervention received. The Safety Analysis Set will be used for all demographic, baseline characteristics, prior/concomitant medication, study drug exposure, and safety analyses.
Full Analysis Set	All participants who took at least 1 dose of study drug and have a valid baseline TETRAS assessment and at least 1 valid post-baseline TETRAS assessment. The Full Analysis Set will be used for the analysis of all efficacy data.
PK Analysis Set	The PK Analysis Set includes all participants who received at least 1 dose of study drug and have at least 1 evaluable plasma concentration. The PK Analysis Set will be used for the analysis of plasma concentrations and PK parameters.

9.3. Statistical Analyses

The SAP will be developed and finalized prior to database lock and will describe the participant populations to be included in the analyses, and procedures for accounting for missing, unused, and spurious data. For all data displays, separate summaries will be generated for each part of the clinical trial. For the randomized portion of Part B, data will be summarized by the randomized

continuation treatment. Safety, tolerability, PK and efficacy variables will be summarized using descriptive statistics. Descriptive summaries for categorical variables will include counts and percentage. Descriptive summaries for continuous variables will include number of participants (n), mean, standard deviation (SD), median, minimum, and maximum. Where appropriate, 95% confidence intervals (CIs) may be reported. Summaries will be presented by time point, where appropriate.

Unless specified otherwise, all data recorded will be listed by participant.

9.3.1. Efficacy Analyses

Reported values and change from baseline values in TETRAS Upper Limb score, TETRAS Performance subscale total and individual scores, TETRAS Upper Limb accelerometer score, TETRAS Upper Limb telehealth score, TETRAS ADL Subscale score, [REDACTED], QUEST total and subscale scores, [REDACTED] will be summarized by time point. In addition, change from baseline scores will also be analyzed using paired t-tests or similar methods. For [REDACTED], reported values will be summarized by time point.

9.3.2. Safety Analyses

Adverse event data will be coded using the Medical Dictionary for Regulatory Activities (MedDRA). The number and percentage of participants experiencing any treatment-emergent AE (TEAE) will be summarized by system organ class (SOC) and preferred term (PT). In addition, TEAEs will be summarized similarly by maximum severity and maximum relationship to PRAX-944. SAEs and TEAEs leading to discontinuation of PRAX-944 will be listed. Reported values and change from baseline values in vital signs, ECG parameters, and hematology and clinical chemistry laboratory parameters will be summarized by time point.

For the C-SSRS, the incidence of suicidal ideation/behavior at any time will be summarized for each C-SSRS ideation, behavior, and ideation/behavior indicator.

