3.2. Part B

Objective	Endpoint
Primary	

 • To evaluate the safety and tolerability of PRAX-944 in participants with ET 	
 • Incidence and severity of AEs • Changes in vital sign measurements • Changes in clinical laboratory results • Changes in ECG parameters • Incidence of C-SSRS measured suicidal ideation or behavior
Secondary	

 • To evaluate the efficacy of PRAX-944 on upper limb tremor in participants with ET 	
 • Change from Baseline to Day 42 in TETRAS Upper Limb score (bilateral sum of items 4a, 4b, and 4c)

 • To evaluate the efficacy of PRAX-944 on other measures of tremor severity in participants with ET 	
 • Change from Baseline to Day 7 and Day 21 in TETRAS Upper Limb score (bilateral sum of items 4a, 4b, and 4c) • Change from Baseline to Day 7, Day 21, and Day 42 in the following: 
 ○ TETRAS Performance subscale total score ○ Accelerometer-based upper limb score (bilateral sum of items 4a, 4b, and 4c) ○ TETRAS Performance individual item scores

Objective	Endpoint

To evaluate the efficacy of PRAX-944 on measures of disease impact in participants with ET	
Change from Baseline to Day 7, Day 21, and Day 42 in the following:
TETRAS ADL subscale scoreQuality of Life in Essential Tremor Questionnaire (QUEST) total and subscale scores

Exploratory

Objective	Endpoint
	

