- E 13. The participant has any of the following at the Screening visit: a serum total bilirubin value $>1.5 \times \text{ULN}$; a serum alanine aminotransferase (ALT) or aspartate aminotransferase (AST) value $>2 \times \text{ULN}$. As an exception, participants that present with elevated bilirubin in the absence of elevations in ALT or AST that fits the pattern of Gilbert's syndrome may be enrolled after discussion with the medical monitor if their conjugated bilirubin is within the ULN.
- E 14. Criterion removed from protocol in Version 5.0.
- E 15. History of any suicide attempt within the past 2 years.
- E 16. History of structural heart disease (eg, congestive heart failure, depressed ejection fraction or left ventricular hypertrophy) or clinically significant cardiac arrhythmias (eg ventricular tachycardia) excluding sinus arrhythmia.
- E 17. History of cancer treated with chemotherapy
- E 18. Any other significant disease, disorder, lab abnormalities, or environmental factor that, in the opinion of the Investigator or Sponsor, may either put the participant at risk due to participation in the clinical trial, may influence or confound the result of the clinical trial, or affect the participant's ability to participate in the clinical trial.
- E 19. Has previously received treatment with PRAX-944 in any clinical trial (including Part A of the current trial for participants enrolling in Part B)

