8.2.5. Columbia-Suicide Severity Rating Scale (C-SSRS) Measurements

The C-SSRS was developed by researchers at Columbia University as a tool to help systematically assess suicidal ideation and behavior in participants during participation in a clinical trial of centrally-acting drugs (Posner 2011). The C-SSRS is composed of 5 questions addressing suicidal behavior and 5 questions addressing suicidal ideation, with sub-questions assessing the severity. Two versions of the C-SSRS will be used in this clinical trial: the Baseline/Screening Version (at the Screening visit) and the Since Last Visit Version (at all other visits). It takes approximately 5 to 10 minutes to administer the C-SSRS. The tool should be administered via interview with the participant (by a trained operator/interviewer).

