- IF the action taken with study drug is “Study drug withdrawn”, THEN set the AE leading to study drug withdrawal flag equal to “Y”.
- OTHERWISE, set the AE leading to study drug withdrawal flag equal to “N”.

Treatment emergent AEs (TEAEs) are defined as those AEs occurring or worsening after the first dose of study drug. If an AE start date is completely missing (ie, in which the day, month, and year are all unknown), then the AE start date will be set to the date of first dose of study drug. For a partial AE start date, the following conventions will be used for imputing the AE start date:

- When the year is present and the month and day are missing:
 - If the year of AE start = the year of first dose of study drug, then the month and day will be set to the month and day of first dose of study drug.
 - If the year of AE start < the year of first dose of study drug, then the month and day will be set to December 31st.
 - If the year of AE start > the year of first dose of study drug, then month and day will be set to January 1st.
- When the year and day are present and the month is missing:
 - If the year of AE start = the year of first dose of study drug, then the month will be set to the month of first dose of study drug.
 - If the year of AE start < the year of first dose of study drug, then the month will be set to December.
 - If the year of AE start > the year of first dose of study drug, then the month will be set to January.
- When the month and year are present and the day is missing:
 - If the year of AE start = the year of first dose of study drug and

- the month of AE start = the month of first dose of study drug, then the day will be set to the day of first dose of study drug.
- the month of AE start < the month of first dose of study drug, then the day will be set to the last day of the month.
- the month of AE start > the month of first dose of study drug, then the day will be set to the 1st day of the month.
- If the year of AE start < the year of first dose of study drug, then the day will be set to the last day of the month.
- If the year of AE start > the year of first dose of study drug, then the day will be set to the 1st day of the month.
- If the imputed AE start date is after the AE stop date, then the AE start date will be set to the AE stop date.

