4.10.6.1 C-SSRS Suicidal Ideation Indicator

A composite indicator of C-SSRS suicidal ideation will be calculated as:

- If the response to any one of the five suicidal ideation questions is “Yes”, THEN set the suicidal ideation indicator equal to 1.
- OTHERWISE, set the suicidal ideation indicator equal to 0.

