5.8.5 C-SSRS

The C-SSRS will be evaluated based on methods described by Nilsson et al. (2013). The number and percentage of participants with any suicidal ideation and/or suicidal behavior following the first dose of study drug will be tabulated.

For the composite endpoint of suicidal ideation, the number and percent of participants who experience any one of the five suicidal ideation events at least once during dosing through follow-up will be tabulated.

For the composite endpoint of suicidal behavior, the number and percent of participants who experience any one of the five suicidal behavior events at least once during dosing through follow-up will be tabulated.

For the composite endpoint of suicidal ideation or behavior, the number and percent of participants who experience any one of the ten suicidal ideation or behavior events at least once during dosing through follow-up will be tabulated.

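### The C-SSRS incidence in SAP 5.8.5 counts any positive answer after first dose and spells out no comparison with the pre-dose interviews, so in the uncontrolled phases persisting ideation counts as on-drug incidence and worsening cannot be seen

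*Protocol*

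**What the plan says.** Protocol 3.2 lists "Incidence of C-SSRS measured suicidal ideation or behavior" among the Part B primary endpoints. In Part A (Protocol 3.1) it is a secondary safety endpoint.

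The count is described in three places:
- Protocol 9.3.2: "For the C-SSRS, the incidence of suicidal ideation/behavior at any time will be summarized for each C-SSRS ideation, behavior, and ideation/behavior indicator".
- SAP 5.8.5, which sets the operative rule: "The number and percentage of participants with any suicidal ideation and/or suicidal behavior following the first dose of study drug will be tabulated". For each of the three composites, the SAP counts participants with an event "at least once during dosing through follow-up will be tabulated".
- SAP 4.10.6.1 to 4.10.6.3, which derive the indicators. The ideation indicator is set to 1 on this condition: "If the response to any one of the five suicidal ideation questions is" positive. Otherwise it is 0. The other two indicators follow the same pattern.

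Pre-dose interviews are collected. Protocol 8.2.5 names two versions of the instrument, "the Baseline/Screening Version (at the Screening visit) and the Since Last Visit Version (at all other visits"). The schedules place pre-dose interviews at Screening and Day 0 in Part A (Table 2), and at Screening and Day 1 in Part B, where the Day 1 interview may be done on Day -1 (Table 3).

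The one exclusion that names suicidality is E 15 in Protocol 5.3: "History of any suicide attempt within the past 2 years". Ideation at Screening or Baseline is not named. E 18 allows discretionary exclusion for other significant conditions.

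For adverse events the SAP does refer back to the pre-dose state (4.10.1): "Treatment emergent AEs (TEAEs) are defined as those AEs occurring or worsening after the first dose of study drug". Laboratory, vital sign and ECG results have change-from-baseline summaries (SAP 5.8.2 to 5.8.4).

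**The concern.** Part A and the Part B titration are open-label with no control group, so a participant's own pre-dose state is the only internal reference for what happens on drug. The other Part B primary safety measures (AEs, vital signs, laboratory tests, ECG) use that reference. The C-SSRS tabulations that the SAP spells out do not.

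Two things are at stake. First, ideation that was there before dosing and is reported again afterwards goes into the on-drug incidence, and the table does not separate it from ideation that began on drug. Second, a participant who was already positive and moves to a more serious category gets the same indicator value as one who did not change, so the count cannot show that kind of signal.

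**Working it through.** The plan gives no C-SSRS figure to reproduce. The check sets the counting rule against possible participant histories and then scales the effect.

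**Inputs**
- Counting rule: SAP 5.8.5 and 4.10.6.
- Interview versions and timing: Protocol 8.2.5, Tables 2 and 3.
- n: about 12 in Part B, with up to 12 more, so 12 to 24 (Protocol 5.1.2). Up to 12 in Part A (Protocol 5.1.1).
- p, the share of enrolled participants with pre-dose ideation: not in the documents. Assumed 3%, 5% and 10%.

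**Step 1. What the rule does with each history**

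| Before first dose | After first dose | Counted under SAP 5.8.5 | New or worsened |
|---|---|---|---|
| None | Ideation | Yes | Yes |
| Ideation | Same category | Yes | No |
| Ideation | More serious category | Yes | Yes |
| Ideation, ended before the baseline interview | None | No | No |

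The first three rows get the same value. The fourth is not counted, because post-dose visits use the Since Last Visit version. One small gap remains in Part B: if the baseline interview is on Day -1, the recall period of the Day 7 interview includes a short pre-dose interval.

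**Step 2. Effect of one carried-over participant**
- n=12: 1/12 = 8.3 percentage points.
- n=24: 1/24 = 4.2 percentage points.

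**Step 3. Chance of enrolling at least one person with pre-dose ideation**

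Formula: 1 - (1 - p)^n.

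| Assumed p | n=12 | n=24 |
|---|---|---|
| 3% | 1 - 0.97^12 = 31% | 1 - 0.97^24 = 52% |
| 5% | 1 - 0.95^12 = 46% | 1 - 0.95^24 = 71% |
| 10% | 1 - 0.90^12 = 72% | 1 - 0.90^24 = 92% |

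**Step 4. What these probabilities mean.** To be counted, an enrolled person with pre-dose ideation must also give a positive answer after dosing. The figures in Step 3 are therefore upper bounds on the chance that at least one carried-over case is counted.

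**The case against.** The other side has several good points.

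- **Cited guide.** SAP 5.8.5 opens by saying that evaluation is based on a published C-SSRS scoring and analysis guide. Its content is not in the documents, so it may cover comparison with baseline. What can be shown is that the SAP does not spell one out. A general citation does not tell the reader which comparison will be tabulated.
- **Other outputs.** Protocol Appendix 2 treats exacerbation of a pre-existing condition as an AE, so worsening ideation recorded as an AE would appear among the TEAEs. SAP 5 lists all recorded data, and with 12 to 24 participants a reader can compare answers by hand. SAP 5.8 also plans safety summaries by visit where applicable, although this does not guarantee a pre-dose C-SSRS row. These points stand as partial mitigation. They do not make the tabulated incidence interpretable by itself.
- **Eligibility.** E 18 and the Screening interview let the investigator or sponsor exclude someone judged at risk. That is discretionary and does not name ideation.
- **Direction of the error.** Counting every post-dose positive answer leans toward over-reporting, which is a defensible choice for safety. This stands, and it is why the all-events count should stay.

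A reader might infer that everyone whose ideation predates PRAX-944 is counted. The documents do not support that: apart from the Day -1 gap, only ideation that persists or recurs after dosing is counted. A reader might also take 46% and 71% as the chance that a carried-over case is counted. They are the chance of enrolling such a person at an assumed 5% prevalence.

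**Conclusion.** The point holds as a gap in the specified tabulation. The SAP's C-SSRS counts do not separate new or worsened ideation or behavior from what was present before dosing, in a measure that is primary for Part B and has no control in Part A or the titration phase. The gap is cheap to close and affects how the result can be read.

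The effect per participant follows from the planned sample sizes and rests on no assumption. The enrolment probabilities rest on an assumed prevalence and on independence between participants, and should be read only as showing that the situation is plausible.

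The importance is moderate. The analysis is descriptive, SAP 5.8 rules out formal safety testing, the sample is one of convenience, and no decision rule is tied to this count. It would be tempting to conclude that a new-or-worsened count should replace the all-events count as the reported incidence. Nothing in the documents requires that, and it would take on-drug ideation out of the headline safety figure.

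**What to change.** In SAP 5.8.5 keep the current all-events counts as the reported incidence. Beside them add:

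1. The number and percentage of participants with ideation or behavior at the pre-dose interviews.
2. The number with new or worsened ideation and, separately, new or worsened behavior, defined as a worst post-dose category above the worst pre-dose category.

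The text should state which pre-dose interviews form the reference (Screening, Baseline or both), the recall period used and the ordering of the categories. The recall period matters because the documents give none for the Screening version, and Screening can last up to 28 days, or 42 for participants stopping primidone.

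The cost is a paragraph of SAP text, a few derived variables and some table rows, all from data already collected. It should be settled before database lock and unblinding, when the SAP is to be final.

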9.3.3. Pharmacokinetic Analyses

For Part A, standard PK parameters will be estimated using noncompartmental methods based on the concentration-time data. These parameters will include, where possible, C_{max} , T_{max} , $t_{1/2}$, $AUC_{0-\tau}$, CL/F , and Vd/F . Exploratory analyses examining the relationship between PK and efficacy parameters may be performed for the PK Analysis Set.

The PK parameters described are those normally calculated for this type of clinical trial; however, the actual parameters calculated may vary depending on the availability and viability of the data obtained. Other parameters may be added as appropriate. Final PK parameters to be reported will be detailed in the SAP or a separate PK analysis plan.

9.3.4. Other Analyses

PK and selected efficacy data may be utilized in a population PK analysis, which will be presented separately from the main clinical study report (CSR).

9.3.5. Interim Analyses

No formal interim analysis is planned for this clinical trial. Clinical trial data from Part A and open-label data from Part B will be reviewed on an ongoing basis.

10. REGULATORY, ETHICAL, AND CLINICAL TRIAL OVERSIGHT CONSIDERATIONS

10.1. Regulatory and Ethical Considerations

This clinical trial will be conducted in accordance with this protocol and with the following:

- Consensus ethical principles derived from international guidelines including the Declaration of Helsinki and Council for International Organizations of Medical Sciences (CIOMS) International Ethical Guidelines
- Applicable International Council for Harmonisation (ICH) Good Clinical Practice (GCP) Guidelines
- Applicable laws and regulations

The protocol, protocol amendments, ICF, IB, and other relevant documents (eg, advertisements) must be submitted to an IRB/IEC by the Investigator and reviewed and approved by the IRB/IEC before the clinical trial is initiated.

Any amendments to the protocol will require IRB/IEC approval before implementation of changes made to the clinical trial design, except for changes necessary to eliminate an immediate hazard to clinical trial participants.

The Investigator will be responsible for the following:

- Providing written summaries of the status of the clinical trial to the IRB/IEC annually or more frequently in accordance with the requirements, policies, and procedures established by the IRB/IEC
- Notifying the IRB/IEC of SAEs or other significant safety findings as required by IRB/IEC procedures
- Providing oversight of the conduct of the clinical trial at the site and adhering to requirements of ICH guidelines, the IRB/IEC, and all other applicable local regulations

10.2. Financial Disclosure

Investigators and sub-Investigators will provide the Sponsor with sufficient, accurate financial information as requested to allow the Sponsor to submit complete and accurate financial certification or disclosure statements to the appropriate regulatory authorities. Investigators are responsible for providing information on financial interests during the course of the clinical trial and for 1 year after completion of the clinical trial.

10.3. Informed Consent Process

The Investigator or his/her representative will explain the nature of the clinical trial to the participant or his/her legally authorized representative and answer all questions regarding the clinical trial.

Participants must be informed that their participation is voluntary. Participants will be required to sign a statement of informed consent that meets the requirements of local regulations, ICH guidelines, and the IRB/IEC or clinical trial center.

The medical record must include a statement that written informed consent was obtained before the participant was enrolled in the clinical trial and the date the written consent was obtained. The authorized person obtaining the informed consent must also sign the ICF.

Participants must be re-consented to the most current version of the ICF(s) during their participation in the clinical trial.

A copy of the ICF(s) must be provided to the participant or the participant's legally authorized representative.

10.4. Data Protection

Participants will be assigned a unique identifier by the Sponsor. Any participant records or datasets that are transferred to the Sponsor will contain the identifier only; participant names or any information which would make the participant identifiable will not be transferred.

The participant must be informed that his/her personal clinical trial-related data will be used by the Sponsor in accordance with local data protection law. The level of disclosure must also be explained to the participant.

The participant must be informed that his/her medical records may be examined by Clinical Quality Assurance auditors or other authorized personnel appointed by the Sponsor, by appropriate IRB/IEC members, and by inspectors from regulatory authorities.

10.5. Data Quality Assurance

All participant data relating to the clinical trial will be recorded on printed or electronic case report forms (eCRFs) unless transmitted to the Sponsor or designee electronically (eg, laboratory data). The Investigator is responsible for verifying that data entries are accurate and correct by physically or electronically signing the case report form (CRF).

The Investigator must maintain accurate documentation (source data) that supports the information entered in the CRF.

The Investigator must permit clinical trial-related monitoring, audits, IRB/IEC review, and regulatory agency inspections and provide direct access to source data documents.

Monitoring details describing strategy (eg, risk-based initiatives in operations and quality such as Risk Management and Mitigation Strategies and Analytical Risk-Based Monitoring), methods, responsibilities and requirements, including handling of noncompliance issues and monitoring techniques (central, remote, or on-site monitoring) are provided in the Monitoring Plan.

The Sponsor or designee is responsible for the data management of this clinical trial including quality checking of the data.

The Sponsor assumes accountability for actions delegated to other individuals (eg, Contract Research Organizations).

Clinical trial monitors will perform ongoing source data verification to confirm that data entered into the CRF by authorized site personnel are accurate, complete, and verifiable from source documents; that the safety and rights of participants are being protected; and that the clinical trial is being conducted in accordance with the currently approved protocol and any other clinical trial agreements, ICH GCP, and all applicable regulatory requirements.

